#### 8. Randomization

After inclusion in the study, the patients are randomly assigned to Group A or Group B. The randomization will be done in two separate groups for genotype 1 and 4 and for genotypes 2 and 3, respectively. In each group, a list with a randomized sequence of A's and B's in blocks of 10 will be used to sequentially assign the patients into groups A or B (appendix 4).

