## 4. Experimental Design

Prospective, randomized, open label pilot study to test the efficacy and safety of a combination treatment with PegIntron, Rebetol, AdoMet and betaine in **non-responders** 

of previous combinations therapy with (peg)IFNα and Ribavirin.

Half of the patients (Group A) will be treated during the first week with AdoMet and Betaine, followed by a combination treatment of PegIntron, Rebetol, AdoMet and Betaine.

The other half of the patients (Group B) will be treated during the first 1 week with PegIntron and Rebetol, followed by a combination treatment of PegIntron, Rebetol, AdoMet and Betaine. (This randomized assignment to groups A or B will allow to test the usefulness of the surrogate marker ISG induction for predicting treatment response). The randomization will be done in two separate groups for genotype 1 and 4 and for genotypes 2 and 3, respectively. In each group, a list with a randomized sequence of A's and B's in blocks of 10 will be used to assign the patients into groups A or B.

The study will be performed at the University Hospital Basel.

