#### 5. Patient Selection

#### **Number of patients:**

30 patients, non-responders to previous (peg-)IFNα - Ribavirin combination therapy

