#### **Duration of treatment**: will depend on HCV-genotype

- 24 weeks for genotypes 2 and 3
- 48 weeks for genotypes 1, 4 and 5

For patients, who do not show an adequate response at week 12 (adequate response at week 12 = drop of HCV RNA of at least 2log or HCV RNA-negativity), treatment can be stopped and the patient enters follow up phase.

**Duration of study:** Will include the treatment period (24 or 48 weeks) as well as the follow-up period of 24 weeks (totally: 48 or 72 weeks)

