## Appendix 4: Randomization List

## **Genotype 1,4**

## Group Date Patient-Initials A В A В В В A A В В В A В A A A A В В

## **Genotype 2,3**

Group	Date	Patient-
		Initials
В		
A		
A		
В		
A		
В		
В		
A		
В		
A		
A		
В		
В		
A		
В		
В		
A		
В		
A		
A

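### The working randomisation list is printed in the protocol of an open-label, single-centre trial, so allocation is not concealed and the A-versus-B comparison of ISG induction is open to selection bias

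*Protocol*

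**What the plan says.** Section 4 describes the trial as a "Prospective, randomized, open label pilot study to test the efficacy and safety" and adds: "The study will be performed at the University Hospital Basel". Section 5 plans for "30 patients, non-responders to previous (peg-)IFNα - Ribavirin combination therapy", split equally between groups A and B.

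Section 8 places the assignment after inclusion. It stratifies by genotype: "The randomization will be done in two separate groups for genotype 1 and 4 and for genotypes 2 and 3, respectively". In each stratum a list in blocks of ten "will be used to sequentially assign the patients into groups A or B (appendix 4".

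Appendix 4 is that list. Under the column heads "Group Date Patient-Initials" it gives the group for each line, already filled in, and leaves the date and the initials to be entered as patients join. There is one such list for genotypes 1 and 4 and one for genotypes 2 and 3.

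Section 7.2 compares groups A and B on ISG mRNA with a Wilcoxon test. Section 7.1 compares sustained response with a published historical rate, and Section 7.2 does the same for the week-12 response.

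The protocol nowhere mentions an independent holder of the list, central release or envelopes.

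**The concern.** Concealment before allocation and blinding after it are separate safeguards. An open-label trial gives up the second but can keep the first. Here the first is missing as well, because the sequence is in a document that the enrolling team holds.

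Genotype is a baseline assessment in Appendices 1a and 1b, so the stratum is known before assignment. With one centre and a list filled from the top, the next free line is known too. Eligibility under Section 5 leaves room for judgement, for example on willingness to comply or on pre-existing conditions that might interfere with participation. Whether a patient is included, and when, can therefore depend on the arm that comes next.

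At stake is the purpose that Section 4 gives for randomising, which is to test ISG induction as a surrogate marker of treatment response. If patients expected to respond well or badly to interferon were steered by arm, a difference in ISG induction could reflect who was placed in each group and not the AdoMet and betaine pretreatment. Each arm holds only about 15 patients (30/2), so a few selectively timed inclusions could matter.

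**Working it through.** **1. Is Appendix 4 the real sequence or only a template?** The plan's own figure for this point is the block size of 10, so each block should hold five A and five B.

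- Genotypes 2 and 3: 20 entries, 10 A and 10 B. Lines 1–10 are 5 A / 5 B and lines 11–20 are 5 A / 5 B.
- Genotypes 1 and 4: 19 legible entries, 9 A and 10 B. The last ten are 5 A / 5 B and the first nine are 4 A / 5 B. Restoring one A anywhere in the first block gives 5/5 in both blocks. This fits one letter lost when the PDF was read and is not counted as an error in the plan.

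Both lists thus behave as a permuted-block sequence drawn by the method of Section 8. Together with the pre-filled group column and the reference in Section 8, this shows that it is the list to be used.

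**2. How predictable is the next allocation?** Three situations, per block of 10 with m = 5 in each arm:

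- *List visible, as planned:* 10 of 10 known in advance, or 100%.
- *List hidden, but block size 10 known and past allocations seen.* The best strategy is to guess the arm with more places left. Expected correct guesses = m + 2^(2m−1)/C(2m, m) − 1/2 = 5 + 512/252 − 0.5 = 6.53 of 10, or about 65%. Allocations known with certainty, once one arm is used up = 2m/(m + 1) = 10/6 = 1.67 of 10. An exact recursion over the remaining A and B places gives the same two values.
- *Simple randomisation:* 50%.

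The second case matters for the remedy. Hiding the list while Sections 4 and 8 still state a fixed block of 10 would leave the guess rate well above 50%.

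**3. Which analyses depend on A versus B?**

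| Endpoint | Comparison in Section 7 | Uses the randomisation? |
|---|---|---|
| Primary: sustained response | All patients against historical 12% | No |
| Secondary 1: week-12 response | All patients against historical 28% | No |
| Secondary 2: ISG induction | Group A against group B, Wilcoxon | Yes |

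**4. Genotype 5, a separate matter.** Section 10.2 sets a duration of "48 weeks for genotypes 1, 4 and 5", and Section 5 does not exclude genotype 5. Sections 4 and 8 and Appendix 4 name only genotypes 1 and 4 and genotypes 2 and 3. The passages need to be reconciled.

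**The case against.** The best defence is that there is little motive to steer patients. The groups differ only in the first week. After it everyone receives the same four drugs, at identical dosages by Section 10.3, so no patient is denied the experimental combination. The endpoint is measured by RT-PCR with a baseline sample for each patient, so a baseline imbalance in ISG level would be visible. This lowers the likely size of any bias and argues against the highest severity. It does not close the route: a baseline ISG value need not show how a patient will respond to interferon, and a laboratory readout guards against biased assessment, not selective inclusion.

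It can also be said that Section 8 assigns only after inclusion. That fixes the order of steps but does not hide the next line. Nor would an unseen analysis plan help, since it could not undo a sequence printed in the protocol.

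A reader might infer more than the document supports:

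- *That the main efficacy result is compromised.* It is not; that comparison does not use A versus B.
- *That bias has occurred or has a known size.* The 100% measures predictability, not bias.
- *That the lists are too short, with about 20 lines each for 30 patients.* This depends on a genotype mix that the protocol does not give. The binomial chance that more than 20 of 30 fall in one stratum is 2% at a 50% share and 94% at an 80% share. A further block could be added by the stated method, and running out would not itself cause bias.
- *That a genotype 5 patient cannot be randomised at all.* The text only fails to name a stratum.

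**Conclusion.** The point holds as a concealment defect confined to secondary endpoint 2, the only analysis that uses the randomisation. As written, the next allocation in either stratum can be read before a patient is included. The protocol thus leaves an open route to selection bias in that comparison, though it does not show that anyone would use it or how large the effect would be.

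The conclusion rests on three things: Appendix 4 is the list in use, as Section 8 says; the enrolling team has the protocol; and no concealment step is described. The 65% figure further assumes that past allocations in the stratum are known and that the guesser plays the best strategy.

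This should be fixed, and before enrolment, because concealment once lost cannot be restored in the analysis. It is not a threat to the primary conclusion. The missing stratum for genotype 5 is a minor inconsistency and adds nothing to the severity.

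**What to change.** 1. Discard the printed sequence and remove it from Appendix 4.
2. Have a new list generated and held outside the enrolling team, by the hospital pharmacy (which already supplies AdoMet and betaine) or by a statistician with no part in enrolment.
3. Release each allocation only after inclusion has been irrevocably recorded, by phone or by sequentially numbered, sealed, opaque envelopes.
4. Use varying block sizes and keep them out of the protocol. Sections 4 and 8 should then describe stratified, blocked randomisation without giving the size.
5. Name the randomisation stratum for genotype 5 in Sections 4 and 8 and in the new list.

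The cost is a few hours of pharmacy or statistician time, one replaced appendix and short edits to Sections 4 and 8. The number of patients, the visits and the endpoints stay as they are.

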#### 9. Patient Discontinuation Criteria:

It is the right and duty of the investigator to interrupt the treatment of any subject whose health or well-being may be threatened by continuation in this study, or who may be experiencing unmanageable factors that may interfere significantly with the study procedures and/or the interpretation of study results. Such subjects should be withdrawn from the study, not continued under a modified regimen.

## 9.1 Subject Discontinuation Criteria

Subject's participation may be terminated for any of the following reasons:

- Serious or life-threatening adverse event (AE).
- Failure to comply with the dosing schedule, study procedures, or other study requirements.
- Subject's request (subjects may discontinue treatment at any time for any reason).
- Pregnancy during the study period.
- The investigator feels that it is in the subject's best interest to discontinue treatment at that time.
- Confirmation that the subject meets the protocol's exclusion criteria with regard to history of psychosis, suicidal ideation, or suicide attempts at any time during the study.

#### 9.2 Procedures for Discontinuation

If a subject withdraws or is removed from the study for any reason prior to the completion of the study, the reason for and date of the discontinuation and date of the last dose of study medication must be recorded in the appropriate section of the Case Report Form (CRF).

At the time of discontinuation, every effort should be made:

- to ensure all procedures and evaluations scheduled for the final treatment visit are performed (see Study Flow Chart), including the assessment of adverse events and medication compliance. Any returned drug must be inventoried.
- to make an appointment for the follow-up visit(s).

## 10. Study Medication and Treatment:

## 10.1. Supply and Drug Dispensing

#### 10.1.1. AdoMet and Betaine

AdoMet (Samyr ®) and Betaine (Cystadane ®) will be supplied by the Pharmacy of the University Hospital Basel.

#### 10.1.2. Pegintron and Rebetol

PegIntron® and Rebetol® will be supplied by Essex Chemie AG. Essex Chemie AG will be informed by fax of the inclusion of a patient, and will then send the supply of PegIntron and Rebetol for 6 months to the study personal of the Division of Gastroenterology and Hepatology of the University Hospital Basel. For patients that have a full 12 month treatment, a second order for PegIntron and Rebetol will be faxed to Essex Chemie AG.

Unused medication will be given back to Essex Chemie AG.

### 10.2. Treatment of Group A Patients:

**Dosage** (dose adjustment guidelines: see Appendix 3): patients included will receive one week of pretreatment with:

1. AdoMet  $3 \times 400 \text{mg/d p.o.}$ 

2. Betaine  $2 \times 3g/d \text{ p.o.}$ 

Followed by a combination treatment with:

- 1. PEG-interferon alfa-2b (PegIntron®): 1.5μg/kg bodyweight s.c./week (independent of genotype) plus
- 2. Ribavirin (Rebetol®):

BW <65 Kg: 800 mg QD (2 capsules in the morning + 2 capsules in the evening)

BW 65-85 Kg: 1,000 mg QD (2 capsules in the morning + 3 capsules in the evening)

BW >85 Kg: 1,200 mg QD (3 capsules in the morning + 3 capsules in the evening)

3. AdoMet 3 x 400mg/d p.o.

4. Betaine  $2 \times 3g/d \text{ p.o.}$ 

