### 10.3. Treatment Group B Patients:

Patients will receive one week of treatment with PegIntron and Rebetol, followed by a combination treatment with PegIntron, Rebetol, AdoMet and betaine. The dosages are identical to group A.

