### 10.4. Dose Modification (for both group A and group B):

Dose modifications should be done as outlined in section 12.2.1.

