#### 12.2.1 Management of Adverse Events

Subjects having AEs will be monitored with relevant clinical assessments and laboratory tests, as determined by the investigator. The investigator is expected to report ongoing AEs at completion of the clinical study to the primary care physician who will determine the need for and provide standard medical care.

Any actions taken and follow-up results must be recorded either on the appropriate page of the CRF or in a follow-up letter to ESSEX Chemie AG as well as in the subject's source documentation. Follow-up laboratory results should be filed with the subject's source documentation.

For all AEs that require the subject to be discontinued from the study, relevant clinical assessments and laboratory tests will be repeated on at least a monthly basis until final resolution or stabilization of the event(s).

Adverse events can be managed by dose reduction of one or both study medications. In the case of life-threatening AEs as described in Section 12.2.4 both PEG-Intron plus REBETOL must be discontinued permanently.

Reduced doses will be achieved by decreasing the injection volume of the PEG-Intron and the number of capsules/tablets of REBETOL as referenced in Table 1 and Table 2. While at a reduced dose level, the subject should return for assessment at a minimum of every two weeks until the AE resolves or the subject is stable. If the AE persists but does not fall into the range for permanent discontinuation, the reduced dose of PEG-Intron and/or ribavirin (whichever has been reduced) may be continued. At the discretion of the investigator, the dose of PEG-Intron and/or ribavirin may be increased to full dose, directly or in steps, when the AE subsides. If the AE recurs, the subject should be maintained at the previously tolerated reduced dose or, at the discretion of the investigator, discontinue treatment.

Table 1 Dose Reduction for REBETOL

Screening Weight a	Full Daily Dose	First Reduced Dose	First Reduced Number of Capsules	Second Reduced Dose	Second Reduced Number of Capsules
40-65 kg	800 mg/day	600 mg/day	1 in AM/2 in PM	400 mg/day	1 in AM/1 in PM
>65-85 kg	1000 mg/day	800 mg/day	2 in AM/2 in PM	600 mg/day	1 in AM/2 in PM
>85-105 kg	1200 mg/day	1000 mg/day	2 in AM/3 in PM	800 mg/day	2 in AM/2 in PM
>106-125 kg	1400 mg/day	1000 mg/day	2 in AM/3 in PM	800 mg/day	2 in AM/2 in PM

a: Use standard rounding procedures: for 0.1-0.4 kg, round down and 0.5-0.9 kg, round up.

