## Appendix 3: Criteria For Major Depressive Episode / DSM-IV™

A. Five (or more) of the following symptoms have been present during the same two-week period and represent a change from previous functioning; at least one of the symptoms is either (1) depressed mood or (2) loss of interest or pleasure.

**Note:** Do not include symptoms that are clearly due to a general medical condition, or mood-incongruent delusions or hallucinations.

- 1. Depressed mood most of the day, nearly every day, as indicated by either subjective report (e.g., feels sad or empty) or observation made by others (e.g., appears tearful). **Note:** In children and adolescents, can be irritable mood.
- 2. Markedly diminished interest or pleasure in all, or almost all, activities most of the day, nearly every day (as indicated by either subjective account or observation made by others)
- 3. Significant weight loss when not dieting or weight gain (e.g., a change of more than 5% of body weight in a month), or decrease or increase in appetite nearly every day. **Note:** In children, consider failure to make expected weight gains.
- 4. Insomnia or hypersomnia nearly every day
- 5. Psychomotor agitation or retardation nearly every day (observable by others, not merely subjective feelings of restlessness or being slowed down)
- 6. Fatigue or loss of energy nearly every day
- 7. Feelings or worthlessness or excessive or inappropriate guilt (which may be delusional) nearly every day (not merely self-reproach or guilt about being sick)
- 8. Diminished ability to think or concentrate, or indecisiveness, nearly every day (either by subjective account or as observed by others)
- 9. Recurrent thoughts of death (not just fear of dying), recurrent suicidal ideation without a specific plan, or a suicide attempt or a specific plan for committing suicide
- B. The symptoms do not meet criteria for a Mixed Episode (see p. 335).
- C. The symptoms cause clinically significant distress or impairment in social, occupations, or other important areas of functioning.

-

Not applicable to this protocol.

- D. The symptoms are not due to the direct physiological effects of a substance (e.g., a drug of abuse, a medication) or a general medical condition (e.g., hypothyroidism).

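### Table 1 in Section 12.2.1 contradicts the ribavirin doses of Section 10.2 at 65 kg (800 versus 1,000 mg/day) and at >106-125 kg (1,400 versus 1,200 mg/day)

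*Protocol*

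**What the plan says.** **Starting dose.** Protocol Section 10.2 gives ribavirin 800 mg/day below 65 kg. The next band is "BW 65-85 Kg: 1,000 mg QD (2 capsules in the morning + 3 capsules in the evening", and the top band, with no upper limit, is "BW >85 Kg: 1,200 mg QD (3 capsules in the morning + 3 capsules in the evening". Section 10.3 applies the same doses to group B: "The dosages are identical to group A".

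**Dose changes.** Section 10.4, which covers both groups, states: "Dose modifications should be done as outlined in section 12.2.1". Section 12.2.1 reduces ribavirin through "the number of capsules/tablets of REBETOL as referenced in Table 1 and Table 2". It also lets the investigator raise a reduced dose again: it "may be increased to full dose, directly or in steps, when the AE subsides".

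**Table 1** is entered by screening weight, rounded to the nearest kilogram by its footnote. Its rows are:

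| Weight | Full dose | First reduction | Second reduction |
|---|---|---|---|
| 40-65 kg | 800 mg | 600 mg | 400 mg |
| >65-85 kg | 1,000 mg | 800 mg | 600 mg |
| >85-105 kg | 1,200 mg | 1,000 mg | 800 mg |
| >106-125 kg | 1,400 mg | 1,000 mg | 800 mg |

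**Cross-reference.** Section 10.2 carries its own pointer, "dose adjustment guidelines: see Appendix 3". Appendix 3 is headed "Criteria For Major Depressive Episode" and contains no dosing rule.

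**The concern.** The protocol holds two weight-to-dose schedules for the same drug, and they differ. Section 10.2 sets what the patient starts on, and Table 1 sets what happens when the dose has to come down. Nothing says which prevails where they disagree, and the pointer in Section 10.2 does not lead to an answer. No entry criterion limits body weight, so both conflicting weights can occur in the trial.

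What is at stake is correct dosing of individual patients. At 65 kg, a scheme meant to work in two graded steps can skip the first one. At the top of the weight range, the table lists as full a dose that Section 10.2 never prescribes.

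**Working it through.** **Step 1. Apply both rules over the weight range.** Inputs are the three bands of Section 10.2, and the four rows and rounding footnote of Table 1. At whole kilograms from 40 to 125 the full doses compare as follows:

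| Weight (kg) | Section 10.2 | Table 1 |
|---|---|---|
| 40-64 | 800 mg | 800 mg |
| 65 | 1,000 mg | 800 mg |
| 66-85 | 1,000 mg | 1,000 mg |
| 86-105 | 1,200 mg | 1,200 mg |
| 106 | 1,200 mg | no row |
| 107-125 | 1,200 mg | 1,400 mg |

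The schedules contradict each other at 65 kg and at 107-125 kg. At 106 kg Table 1 is silent, as it is below 40 kg and above 125 kg.

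**Step 2. Effect at 65 kg.** The patient starts on 1,000 mg, which is 1,000/65 = 15.4 mg/kg.
- First reduction by the 40-65 kg row: (1,000 - 600)/1,000 = 40%. By the row that starts from 1,000 mg: (1,000 - 800)/1,000 = 20%.
- Second reduction by the 40-65 kg row: (1,000 - 400)/1,000 = 60% below the start, 400/65 = 6.2 mg/kg. By the 1,000 mg row: (1,000 - 600)/1,000 = 40%, 600/65 = 9.2 mg/kg.

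**Step 3. Width of the 65 kg window.** Table 1 treats 64.5-65.4 kg as 65 kg. Section 10.2 states no rounding, so as written 64.5-64.9 kg gets 800 mg under both rules and the conflict covers 65.0-65.4 kg. If Section 10.2 were rounded in the same way, the window would be 64.5-65.4 kg.

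The missing rounding rule also matters at 85.1-85.4 kg. Unrounded, Section 10.2 gives 1,200 mg, while Table 1 rounds to 85 kg and uses the 1,000 mg row. The first reduction would then be to 800 mg, (1,200 - 800)/1,200 = 33%, instead of to 1,000 mg, (1,200 - 1,000)/1,200 = 17%. A common rounding rule removes this mismatch.

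**Step 4. Effect at >106-125 kg (106.5-125.4 kg after rounding).**
- Reductions go to 1,000 and then 800 mg, the same as in the >85-105 kg row. They agree with a start on 1,200 mg.
- The listed full dose is 1,400/1,200 = 1.17 times the prescribed dose, or 17% higher.
- At 107 kg: 1,400/107 = 13.1 against 1,200/107 = 11.2 mg/kg. At 125 kg: 1,400/125 = 11.2 against 1,200/125 = 9.6 mg/kg.

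**Step 5. Check against the overdose limit.** Section 12.10 defines a ribavirin overdose as more than 20 mg/kg/day. The highest figure in steps 2 to 4 is 15.4 mg/kg, so none of the conflicting doses reaches that limit.

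**The case against.** **The 65 kg conflict is only a boundary convention.** A user might match the patient's current dose to the full-dose column, find the 1,000 mg row and reduce to 800 mg, which is right. That is a sensible way to read the table. But the table is keyed by screening weight, and by that key a 65 kg patient lands in the 800 mg row. The protocol does not say that dose overrides weight. The narrowness of the window stands and limits the size of the point.

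**The 1,400 mg entry is inert.** A reader might infer that the protocol directs re-escalation to 1,400 mg. The text does not support that. The table is titled and invoked for reductions, and the re-escalation sentence does not cite it. For a patient reduced from 1,200 mg, full dose most naturally means 1,200 mg. Full-dose capsule counts appear only in Section 10.2, and no capsule schedule for 1,400 mg exists anywhere. This objection stands. What remains is a wrong cell in the full-dose column of a table consulted when doses change, so misreading is possible but not prescribed.

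**The Appendix 3 pointer is merely stale.** This is largely right, since Section 10.4 does send the reader to Section 12.2.1. The pointer still needs correcting, but it leaves nobody without direction.

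**Conclusion.** Table 1 is wrong as written at two places when set against Section 10.2. At 65 kg (65.0-65.4 kg with Section 10.2 as it stands), lookup by weight turns the first reduction from 20% into 40% and the second from 40% into 60% below the starting dose. At >106-125 kg the listed full dose is 200 mg (17%) too high. The reductions in that band are correct, and harm would require a misreading of the re-escalation sentence.

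The point is minor and concerns patient safety and dosing consistency. The size at 65 kg assumes that staff enter Table 1 by screening weight, as its row key implies. The protocol plans 30 patients and gives no weight distribution, so the number affected cannot be derived from it. Given the narrow window at 65 kg and a high weight band where only a misreading matters, it should be small.

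A reader might infer that inconsistent dosing compromises the sustained virologic response result. The documents do not support that: the conflict applies equally to groups A and B, and it enters neither the sample-size formula nor the comparison with the historical rate.

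**What to change.** - **Table 1:** use the bands of Section 10.2, namely <65, 65-85 and >85 kg with no upper limit. Full doses are 800, 1,000 and 1,200 mg/day, first reductions 600, 800 and 1,000 mg/day, and second reductions 400, 600 and 800 mg/day.
- **Rounding:** state one weight-rounding rule and apply it in both Section 10.2 and Table 1.
- **Cross-reference:** point Section 10.2 to Section 12.2.1 instead of Appendix 3.
- **If 1,400 mg is intended:** add that band, with its capsule schedule, to Section 10.2, and close the gaps in Table 1 at 106 kg and above 125 kg.

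The cost is a short protocol amendment to one table and a few words in Section 10.2. It needs no extra patients, visits or procedures.
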